10.1.4. Administration of XmAb18087

XmAb18087 administration should begin as soon as possible after the dosing solution is made. If there is a delay in administration, it

The full-calculated dose will be

administered based on the subject's actual baseline weight measurement in kilograms. Following the first dose, subsequent doses will only be modified if the subject's weight changes by more than 10% from the Day -1 weight at which point it will be recalculated using the current weight.

XmAb18087 should not be administered as an IV push or bolus.

Study drug will be administered as an open-label solution at a constant rate period. Precautions for CRS or infusion reactions or anaphylaxis should be observed during XmAb18087 administration. Due to the possibility that CRS, allergic reactions, or infusion reactions may occur, emergency resuscitation equipment (a "crash cart") and medications including steroids and tocilizumab should be present in the immediate area where subjects are receiving their infusions. Additional supportive measures should be available and may include, but are not limited to: acetaminophen, antihistamines, corticosteroids, IV fluids, bronchodilators, epinephrine, vasopressors, oxygen, and tocilizumab. Please refer to Section 11.3 or Appendix C for management of infusion reactions, CRS, and neurologic toxicities.

Vital signs will be measured and recorded as follows: immediately (within 60 minutes) prior to the infusion; during the infusion at 15, 30, and 60 minutes (± 5 minutes for each time point) from start time of the infusion; immediately (within 5 minutes) before EOI; and at 15, 30, and 60 minutes (± 5 minutes for each time point), then hourly (± 5 minutes) for a 3-hour period, after EOI. Oxygen saturation levels will be captured with each vital sign collection; however, pulse oximetry monitoring must be maintained continuously throughout the entire admission or observation period for each administration of XmAb18087. All supportive measures consistent with optimal subject care will be provided throughout the study according to institution standards. For subjects who a) tolerate 3 consecutive infusions without an infusion reaction during the observation period and b) have completed 4 infusions at the highest dose for that subject, the postinfusion observation period and vital signs assessment may be reduced from 4 hours to 2 hours.

10.2. Pembrolizumab (Keytruda®)

Pembrolizumab is an FDA-approved humanized monoclonal antibody that blocks the interaction between PD1 and its ligands, PDL1 and PDL2.

10.2.1. Administration of Pembrolizumab

In dosing cohorts incorporating pembrolizumab (Part B only), pembrolizumab will be administered by IV infusion on Days 15 and 36 of each 42-day cycle. Pembrolizumab will be provided by sites as standard of care for advanced MCC.

Version 1.0 Page 74 of 145

Vital signs associated with the pembrolizumab infusion will be measured and recorded as follows: immediately prior (within 10 minutes before blood sampling) to the start of the infusion; during the infusion at 5 and 15 minutes (\pm 2 minutes) from the start time of the infusion; immediately (within 2 minutes) before the EOI; and at 15 minutes (\pm 2 minutes) after EOI. During Cycle 1, the subject will be observed for 4 hours after the infusion. On subsequent pembrolizumab administration days, the subject may be discharged 15 minutes postinfusion, if stable.

Pembrolizumab will be administered at a dose of 400 mg using a 30-minute IV infusion. Sites should make every effort to target infusion timing to be as close to 30 minutes as possible. However, given the variability of infusion pumps from site to site, a window between -5 minutes and +15 minutes is permitted (ie, infusion time is 30 minutes [-5 minutes/+15 minutes]). For additional information, refer to the pharmacy manual and the pembrolizumab prescribing information (Keytruda[®] Package Insert, 2020).

Pembrolizumab injection is a sterile, preservative-free, clear to slightly opalescent, colorless to slightly yellow solution that requires dilution for IV infusion. Each vial contains 100 mg of pembrolizumab in 4 mL of solution. Each 1 mL of solution contains 25 mg of pembrolizumab and is formulated in: L-histidine (1.55 mg), polysorbate 80 (0.2 mg), sucrose (70 mg), and Water for Injection, USP.

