5.2.3. Justification for Pembrolizumah Dose

The planned dose of pembrolizumab for this study is 400 mg every 6 weeks (Q6W), which is a current FDA-approved dose for adults with recurrent locally advanced or metastatic MCC (Keytruda® Package Insert, 2020).

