7.3. Dosing Schedule

Each subject will be administered XmAb18087 IV at a constant infusion rate over

Version 1.0 Page 44 of 145

The initial treatment period for each subject in this study is 1 cycle. Each cycle is 42 days long. In Part A and Part C, each cycle will consist of 6 weekly doses of XmAb18087 (on Days 1, 8, 15, 22, 29, and 36).

In Part B, each cycle will consist of 5 XmAb18087 doses on Days 1, 8, 22, 29, and 36. Pembrolizumab will be administered as 1 dose during each 42-day cycle, on Day 15.

Part A dose levels are defined in Table 2. Part B dose levels are defined in Table 3. Part C dose levels are defined in Table 4.

The dose is based on the subject's actual baseline weight measurement in kilograms (rounded to the nearest integer) on Day -1. Following the first dose at any dose level, the weight used for calculation of subsequent doses will be modified only if the subject's weight changes by more than 10% from the baseline weight, at which point the dose will be recalculated using the current weight (rounded to the nearest integer).

Version 1.0 Page 45 of 145

Table 2: Part A (MCC) Monotherapy Safety Run-in and Expansion Cohorts

					Cycle	e 1						Cycle	2+			Subjects
	Cycle and Day	D1	D8	D15	D22	D29	D36	D40	D1	D8	D15	D22	D29	D36	D40	
	•							± 2							± 2	
	Drug			XmA	b1808	7		EA			XmAb	18087			EA	
				(με	g/kg)						(μg/	kg)				
	1	8	15	22	29	36	40	43	50	57	64	71	78	82		
Part A	1A	0.3	1.0	1.0	1.0	1.0	1.0		1.0	1.0	1.0	1.0	1.0	1.0		3 - 6
(Safety	2A	0.3	1.0	2.0	2.0	2.0	2.0		2.0	2.0	2.0	2.0	2.0	2.0		3 - 6
Run-in)	3A	0.3	1.0	2.0	4.0	4.0	4.0		4.0	4.0	4.0	4.0	4.0	4.0		3 - 6
Part A (Expansion)	Expansion A							At	RD coho	rt						Up to 22

D = day; EA = efficacy assessment (no drug administered); MCC = Merkel cell carcinoma; RD = recommended dose. Maximum escalated dose for each cohort in bold.

Version 1.0 Page 46 of 145

Table 3: Part B (MCC) Combination Therapy Safety Run-in and Expansion Cohorts

	Cycle			(Cycle 1						(Cycle 2	+			Subjects
	and Day	D1	D8	D15	D22	D29	D36	D40	D1	D8	D15	D22	D29	D36	D40	
								± 2							± 2	
	Drug	XmAb (μg/		Pem (mg)	X	mAb18 (μg/kg		EA	XmAb (μg/		Pem (mg)	X	mAb18 (μg/kg		EA	
	Study Day	1	8	15	22	29	36	40	43	50	57	64	71	78	82	
	1B	0.3	0.3	400	0.3	0.3	0.3		0.3	0.3	400	0.3	0.3	0.3		3 - 6
Part B	2B	0.3	1.0	400	1.0	1.0	1.0		1.0	1.0	400	1.0	1.0	1.0		3 - 6
(Safety Run-in)	3B	0.3	1.0	400	1.0	2.0	2.0		2.0	2.0	400	2.0	2.0	2.0		3 - 6
	4B	0.3	1.0	400	1.0	2.0	2.0		2.0	4.0	400	4.0	4.0	4.0		3 - 6

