- f XmAb18087 is administered on Day 15 in Parts A and C only. Pembrolizumab is administered on Day 15 of each cycle in Part B only. XmAb18087 is NOT to be administered on Day 15 in Part B. Pembrolizumab will be provided by sites as standard of care.
- g Complete medical history and PE is to be performed at Screening. For all the other time points, only an abbreviated, symptom-directed PE is to be performed.
- May be performed up to 24 hours prior to infusion. The following procedures that are completed on Day -1 within 24 hours of Cycle 1 Day 1 dosing do not need to be repeated on Cycle 1 Day 1: PE, ECOG, and local safety laboratories (eg, CBC with differential and platelets, chemistry panel, coagulation panel, and urinalysis). These safety laboratory assessments will be performed by the central laboratory and should also be performed by local clinical site laboratories so that clinical site personnel can review results before administering XmAb18087.
- Baseline neurologic examination to be performed on Day -1. If a subject appears to be experiencing neurologic toxicity, the neurologic examination should be repeated as necessary to evaluate the subject's condition. Guidelines on management of neurologic toxicity are included in both Section 11.3.3.4 and Appendix C.
- Supine blood pressure and pulse rate, body temperature, respiratory rate, and blood oxygen saturation by pulse oximetry. On days of XmAb18087 infusions, vital signs should be taken within 60 minutes of predose; 15, 30, and 60 minutes after start of infusion (± 5 minutes for each time point); immediately (within 5 minutes) before EOI; 15, 30, and 60 minutes after EOI (± 5 minutes for each time point); and then hourly (± 5 minutes) for 3 hours. When possible, vitals should be measured before blood sampling. Oxygen saturation levels will be captured with each vital sign collection; however, pulse oximetry monitoring must be maintained continuously throughout the entire admission or observation period for each administration of XmAb18087. For information on management of oxygen saturation of 90% or lower, see Section 11.3.3.1. All vital signs during infusion should be taken with the subject in the same position. On nondosing days, vitals should be measured before blood sampling.

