- Non days of pembrolizumab infusions, vital signs should be taken immediately prior (within 10 minutes before blood sampling) to the start of infusion; during the infusion at 5 and 15 minutes (± 2 minutes); immediately (within 2 minutes) before the EOI; and at 15 minutes (± 2 minutes) after EOI.
- On days when XmAb18087 is infused, electrocardiograms should be taken prior to infusion, 2 to 4 hours after EOI, and if clinically indicated.
- $^{\rm m}$ $\,$ Part B only: ECGs are not performed on days when pembrolizumab is administered.

receptor 2.

- ⁿ Once postmenopausal status has been established by FSH, this test need not be repeated during the clinical trial.
- In Cycle 1, whole blood for flow cytometry (FACS) analysis will be obtained predose on Day 1 (± 1 hour); on Day 2 (24 hours post-EOI ± 3 hours); on Day 3 (48 hours post-EOI ± 3 hours); predose on Day 8 ± 1 hour; on Day 9 (24 hours post-EOI ± 3 hours); on Day 10 (48 hours post-EOI ± 3 hours); predose on Day 15 ± 1 hour; predose on Day 22 ± 1 hour; predose on Day 29 ± 1 hour; predose on Day 36 ± 1 hour; on Day 37 (24 hours post-EOI ± 3 hours); on

Version 1.0 Page 58 of 145

- Day 38 (48 hours post-EOI \pm 3 hours); and on Day 39 (72 hours post-EOI \pm 3 hours). In **Cycles 2 and higher**, whole blood for FACS will be obtained predose on Day 22 \pm 2 days and on Day 36 \pm 2 days. **Upon discontinuation from the study**, whole blood for FACS analysis should be obtained at EOT (\pm 2 days), at 14 days post-EOT (\pm 2 days), and at the 28 days post-EOT visit(\pm 2 days.)

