- In **Cycle 1**, serum for cytokine profile analysis will be obtained predose on Day 1, 8, and 36 and at 5 minutes (± 1 minute), 1 hour (± 10 minutes), 2 hours (± 10 minutes), 4 hours (± 10 minutes), 7 hours (± 10 minutes), and 10 hours (± 10 minutes) post-EOI; on Days 2, 9, and 37 (24 hours post-EOI ± 3 hours), Day 3, 10, and 38 (48 hours post-EOI ± 3 hours), and on Day 39 (72 hours post-EOI ± 3 hours). Additionally, samples will be collected predose on Days 15, 22, and 29 and at 5 minutes (± 1 minute), 1 hour (± 10 minutes), 2 hours (± 10 minutes), 4 hours (± 10 minutes), and 7 hours (± 10 minutes) post EOI. In **Cycle 2 and higher**, serum for cytokine profile analysis will be obtained on Day 1 and Day 22 (± 2 days) of each cycle predose and at 1 hour (± 10 minutes), 2 hours (± 10 minutes), and 4 hours (± 10 minutes) post EOI. Serum should also be drawn at any time there is clinical suspicion of cytokine release syndrome and repeated 4 hours later.
- ^q Polyoma virus assay serum collection is for Part A and Part B only.
- ^r Including serum, peripheral blood, and nucleic acid samples.
- s Optional; by specific subject consent.
- In **Cycle 1**, serum for PK analysis will be obtained at Day -1; on Days 1 and 36 predose and at 5 minutes (± 1 minute), 1 hour (± 10 minutes), 2 hours (± 10 minutes), 4 hours (± 10 minutes), 7 hours (± 10 minutes), and 10 hours post-EOI (± 10 minutes, Day 1 only); on Days 2 and 37 (24 hours post-EOI ± 3 hours), and Days 3 and 38 (48 hours post-EOI ± 3 hours), and Day 39 (72 hours post-EOI ± 3 hours); on Day 8 predose and at 5 minutes (± 1 minute) post-EOI; on Day 10 (48 hours post-EOI); and on Days 15, 22, and 29 predose and at 5 minutes post-EOI (± 1 minute). In **Cycles 2 and higher**, serum for PK analysis will be collected on the first day of each cycle (± 2 days) predose and 5 minutes (± 1 minute) post-EOI (all subjects). Subjects in Part B only (combination therapy) will also have serum collected for PK analysis on Day 15 at predose and 5 minutes (± 1 minute) post-EOI. Upon **discontinuation from the study**, serum for PK analysis should be obtained at the EOT visit (± 2 days), the 14-day post-EOT visit (± 2 days), and the 28 day post-EOT visit (± 2 days).

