9. TREATMENT OF SUBJECTS

9.1. Identity of Study Treatments

XmAb18087 is a humanized bsAb that binds both CD3 and the tumor antigen SSTR2 to recruit cytotoxic T cells that will kill SSTR2⁺ tumor cells. Intravenous Stabilization Solution is a concentrated form of the XmAb18087 buffer that minimizes protein binding to the administration equipment.

Prior to dilution, the vial containing parenteral drug product should be inspected visually. If particulate matter and/or discoloration are noted, drug should not be administered, and the Sponsor should be notified.

Pembrolizumab (Keytruda[®]) is an approved humanized mAb targeting the cell surface antigen PD1. It will be administered at the dose and schedule of 400 mg IV over 30 minutes every 6 weeks. It is supplied as a 100 mg per 4 mL (25 mg/mL) solution in a single-dose vial. Pembrolizumab is provided by sites as standard of care for advanced MCC.

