10.4.4. Packaging and Labeling of Pembrolizumab

Pembrolizumab will be obtained from commercial sources and administered to subjects in the combination therapy cohorts on Day 15 of each 42-day cycle as directed by the package insert (Keytruda® Package Insert, 2020).

Version 1.0 Page 76 of 145

Xencor, Inc

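### Protocol Section 10.2.1 orders pembrolizumab on Days 15 and 36 of each cycle, doubling the one 400 mg dose per cycle set everywhere else

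*Protocol*

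**What the plan says.** Section 10.2.1 of the protocol states that in the Part B cohorts "pembrolizumab will be administered by IV infusion on Days 15 and 36 of each 42-day cycle". Later in the same section each infusion is set at 400 mg over 30 minutes.

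The rest of the plan describes a different schedule:

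- Section 7.3 (Dosing Schedule): "Pembrolizumab will be administered as 1 dose during each 42-day cycle, on Day 15".
- Table 7, footnote f: "Pembrolizumab is administered on Day 15 of each cycle in Part B only".
- Section 10.4.4: the drug goes to the "combination therapy cohorts on Day 15 of each 42-day cycle as directed by the package insert".
- Section 9.1: "It will be administered at the dose and schedule of 400 mg IV over 30 minutes every 6 weeks". Section 5.2.3 justifies the same 400 mg every-6-weeks regimen as a current FDA-approved dose.

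Day 15 alone also appears in the Synopsis (Methodology, Treatment Plan, Duration of Treatment and Cohort Table B), Section 7.1, Table 3, the body of Table 7, Section 7.10, and SAP Section 4.1. The evaluable population (Synopsis, Protocol Section 14.4 and SAP Section 7) counts one pembrolizumab dose in a Part B cycle.

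**The concern.** Section 10.2.1 is where a site would look to see how pembrolizumab is given, and sites supply the drug themselves. Section 17.4 requires the protocol to be followed exactly, which cannot be done when Sections 7.3 and 10.2.1 give different schedules.

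If Section 10.2.1 were followed, four things would go wrong:

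- **Dose.** Exposure would be twice the regimen justified in Section 5.2.3.
- **Dose-finding.** The second infusion would fall in Cycle 1, after which the Safety Review Committee reviews each run-in cohort (Section 7.7). In Part B, an immune-related event that forces permanent discontinuation is an adverse event of specific concern (Section 7.8), and stopping pembrolizumab also stops XmAb18087 (Section 10.3.2). Unplanned exposure could therefore affect the choice of recommended dose.
- **Cycle definition.** Two pembrolizumab doses do not match the Part B cycle used to define the evaluable population.
- **Assessments.** Day 36 is an XmAb18087 infusion day in every Part B cohort. Table 7 and its footnote l call for ECGs on such days, yet footnote m reads "Part B only: ECGs are not performed on days when pembrolizumab is administered".

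**Working it through.** **Inputs**

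| Item | Value | Source |
|---|---|---|
| Dose per infusion | 400 mg | Protocol 10.2.1 |
| Infusion days as written | Days 15 and 36 | Protocol 10.2.1 |
| Infusion day elsewhere | Day 15 | Protocol 7.3, Table 3, Table 7 |
| Cycle length | 42 days | Protocol 7.3 |
| Planned regimen | 400 mg every 6 weeks | Protocol 5.2.3 and 9.1 |
| Overdose limit, per dose | 2000 mg, or at least 5 times the indicated dose | Protocol 10.2.2 |
| Enrolled | 4 in all: 2 in Part A, 2 in Part C | SAP 5.1 |

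**1. Reproduce the plan's regimen.** Day 15 only gives 1 × 400 = 400 mg per cycle. Day 15 of Cycle 2 is study day 42 + 15 = 57, so the interval is 57 − 15 = 42 days, or 6 weeks. This agrees with Sections 5.2.3 and 9.1.

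**2. Apply Section 10.2.1 as written.**

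- Dose per cycle: 2 × 400 = 800 mg.
- Ratio to plan: 800 / 400 = 2.
- Study days in Cycles 1 and 2: 15, 36, 42 + 15 = 57 and 42 + 36 = 78.
- Intervals: 36 − 15 = 21, 57 − 36 = 21 and 78 − 57 = 21 days.

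The text therefore describes 400 mg every 3 weeks, which does not agree with the plan.

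**3. Look for support for Day 36.** None was found. Table 3 shows XmAb18087, not pembrolizumab, on Day 36 of every Part B cohort, and no cohort table puts both drugs on one day. For Cycles 2 and higher, footnote t says Part B subjects "will also have serum collected for PK analysis on Day 15 at predose and 5 minutes" after infusion; no matching sample is added on Day 36. Footnotes l, m and t fit together when pembrolizumab is given on Day 15 and not when it is also given on Day 36. They are evidence of which schedule was meant, not further errors.

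**4. Would the overdose rule catch it?** The rule applies to a single dose. The Day 36 infusion would be 400 mg, and 400 / 2000 = 0.20 of the limit, the same as any correct dose. It would not be flagged.

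**5. Subjects affected.** Part B enrolment: 4 − 2 − 2 = 0.

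**The case against.** The case for treating this as minor has substance. The intended regimen is not in doubt: Section 7.3 is the designated dosing schedule, Table 3 agrees with it, and the single-dose or every-6-weeks schedule is repeated throughout. Section 10.2.1 itself speaks of observation after the infusion in the singular during Cycle 1, and refers sites to the pharmacy manual and prescribing information. A site would have to override all of that to give a second dose, and the likelier outcome is a query to the sponsor. The study was stopped before Part B enrolled anyone, and the SAP now plans only listings, so no estimate, count or decision changes. The overdose rule was also not designed to detect schedule errors, so its silence adds little.

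All of this is correct, and it limits the practical consequence. It does not make the sentence right. The sentence is complete and unambiguous, it stands in the section that governs administration, and a reader who consults only that section would give twice the planned drug.

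**Conclusion.** The inconsistency is real and Section 10.2.1 is the outlier. As written it orders 800 mg per 42-day cycle at 21-day intervals, against 400 mg at 42-day intervals in the rest of the plan, a two-fold difference. The 800 mg figure is not printed in the protocol; it follows from two infusions at the 400 mg set in the same section.

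It should be treated as a necessary correction because of the type of error, a wrong dosing instruction, and not because of any harm done. Relying on the enrolment reported in the SAP, no subject was exposed to it and no analysis is affected.

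**What to change.** In Section 10.2.1, remove Day 36 so that the sentence gives Day 15 of each 42-day cycle as the only pembrolizumab day. No other section needs to change to agree with it. With the study closed, correct or annotate the text of record and do not carry the sentence into any later protocol. The cost is a wording change, with none in patients or analysis.

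Two minor slips in the Synopsis Treatment Plan, both about XmAb18087, can be corrected at the same time:

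- **Cohort 4B:** Day 1 of later cycles is listed at both 2.0 and 4.0 µg/kg. Remove it from the 4.0 µg/kg list, since Table 3 gives 2.0.
- **Cohort 3A:** a list of first-cycle dosing days is repeated. Delete the repetition to match Table 2.

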10.2.2. Treatment of Overdose

For this study, an overdose of pembrolizumab will be defined as any dose of 2000 mg or $\geq 5 \times$ the indicated dose.

No specific information is available on the treatment of overdose of XmAb18087, or of pembrolizumab. In the event of overdose of either drug, the participant should be observed closely for signs of toxicity. Appropriate supportive treatment should be provided if clinically indicated.

10.3. Safety Criteria for Dose Adjustment or Stopping Dose

10.3.1. Criteria for Adjustment or Stopping Dose of XmAb18087

Subjects experiencing a significant toxicity should be treated with standard medical interventions (eg, acetaminophen for fever) as appropriate.

For guidelines on management of infusion reactions/CRS/neurologic toxicity, and rules regarding study drug adjustment/discontinuation after an infusion reaction/CRS/neurologic toxicity, see Section 11.3.3 or Appendix C.

Subjects experiencing an AE that meets AESC criteria (as defined in Section 7.8 above) will have subsequent dosing held until recovery to baseline or ≤ Grade 2 following the AE. In the event that a > Grade 2 drug-related toxicity persists > 14 days and/or 2 consecutive doses are missed, the subject will be permanently discontinued from the study drug treatment. Subjects who experience the same AE that meets AESC criteria on 2 consecutive infusions will be subsequently treated at one dose level lower than the dose at which the AE occurred. Rechallenge with study drug is not permitted for any Grade 4 toxicity.

Version 1.0 Page 75 of 145

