Should the study be terminated and/or the site closed for whatever reason, all documentation pertaining to the study and IMP must be returned to the Sponsor. Any actions required for assessing or maintaining subject safety will continue as required, despite termination of the study by the Sponsor.

Treatment Plan:

Part A, which will enroll subjects with previously treated advanced MCC, consists of safety-run in cohorts followed by an expansion cohort. For the first safety run-in cohort (Cohort 1A), 3 to 6 subjects will be enrolled and will receive step-up dosing as follows: 0.3 μg/kg on Day 1, followed by 1.0 μg/kg on Days 8, 15, 22, 29, and 36 of the first cycle, and Days 1, 8, 15, 22, 29, and 36 of all subsequent cycles. If the Cohort 1A regimen is not tolerated, lower dose levels may be explored. If the Cohort 1A regimen is tolerated, 3 to 6 subjects will be enrolled in Cohort 2A and will receive step-up dosing as follows: 0.3 μg/kg on Day 1, 1.0 μg/kg on Day 8, and 2.0 μg/kg on Days 15, 22, 29, and 36 of the first cycle and Days 1, 8, 15, 22, 29, and 36 of all subsequent cycles. If this regimen is tolerated, 3 to 6 subjects will be enrolled in Cohort 3A and will receive step-up dosing as follows: 0.3 μg/kg on Day 1, 1.0 μg/kg on Day 8, 2.0 μg/kg on Day 15, and 4.0 μg/kg on Days 22, 29, and 36 of the first cycle and Days 1, 8, 15, 22, 29, and 36 of the first cycle and Days 1, 8, 15, 22, 29, and 36 of all subsequent cycles. See Cohort Table A.

Based on assessments of tolerability, safety, and PK data from all the safety run-in cohorts in Part A, an RD regimen for expansion will be selected. Up to 9 subjects will be enrolled at the RD. If at least 1 subject shows a response by RECIST 1.1 criteria, then enrollment will continue up to a total of 22 subjects to evaluate efficacy.

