7.7. Safety Run-in Cohorts

In each safety run-in cohort, no more than 1 subject will be initiated on treatment with XmAb18087 on any given day.

The planned initial XmAb18087 dose for all cohorts is $0.3 \,\mu\text{g/kg}$. Subsequent doses will then be escalated in steps (except for Cohort 1B, which will use $0.3 \,\mu\text{g/kg}$ for all doses) as indicated in Table 2, Table 3, and Table 4 in an effort to reduce the incidence and severity of CRS.

For all safety run-in cohorts in Part A, Part B, and Part C, the SRC will decide whether to advance to the next higher dose level cohort based on review of all available safety data. For each cohort, 3 subjects will be initially enrolled. If no subject experiences an adverse event of specific concern (AESC, as defined in Section 7.8 below), the SRC will be convened after all 3 subjects have completed one treatment cycle or discontinued treatment, whichever comes first. If 1 of the initial 3 subjects experiences an AESC, 3 additional subjects will be enrolled in that cohort (up to a total of 6 subjects) prior to convening the SRC. If 2 subjects experience an AESC, no additional subjects will be enrolled until the SRC has convened and made a recommendation based on the available safety data. Based on the type and severity of toxicities observed, the SRC may modify the safety run-in scheme (eg, decreases in dose level, smaller escalation steps, or other changes in the regimen), as long as the changes do not significantly affect the risk profile of the study.

If a subject discontinues treatment prior to completion of the first cycle due to an AE, that subject will not be replaced. If a subject discontinues treatment prior to completion of the first cycle for any other reason, an additional subject may be enrolled as a replacement.

Part A will begin by enrolling 3 to 6 subjects in Cohort 1A. After Cohort 1A dosing is demonstrated to be tolerable and is approved by the SRC, Part B will begin by enrolling Cohort 1B, which is one dose level lower than Cohort 1A.

Part C may begin concurrently with Part A.

The safety run-in portion will continue until establishment of an RD for expansion or until the repeated dose level reaches the highest dose planned in this study.

Enrolling additional subjects beyond 142 will require a protocol amendment.

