^d Intracranial hemorrhage with or without associated edema is not considered a neurotoxicity feature and is excluded from ICANS grading. It may be graded according to CTCAE v5.0 (Lee, 2019).

Clinical management of neurotoxicity consists of the following:

- Monitor subjects closely for signs and symptoms of these events (including administration of mental status and neurologic examinations when these seem clinically warranted).
- If neurotoxicity becomes evident, a blood sample for cytokine analysis should be drawn at that time, and again 4 hours later, in addition to scheduled cytokine monitoring if already in progress.
- If neurologic toxicity is Grade 4, discontinue XmAb18087, if still infusing.
- For Grade 3 neurologic toxicity, withhold both drugs until the toxicity has recovered to ≤ Grade 1 (mild) and has remained at ≤ Grade 1 for at least 3 days before restarting therapy. Restart XmAb18087 at 75% of the previous dose. Restart pembrolizumab at the full dose. Escalate back to full dose at the time of the next dose if ≥ Grade 2 toxicity does not recur. If ≥ Grade 2 toxicity reoccurs at 75% dose, or if < Grade 2 toxicity takes more than 7 days to resolve, discontinue permanently.
- For severe neurologic symptoms, administer additional dexamethasone 10 mg intravenously and repeat every 12 hours if symptoms do not abate rapidly, or treat according to the clinical site's institutional protocol for such reactions.
- For recurrent seizures, anticonvulsant therapy may be necessary.

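### After an AESC hold with one missed dose, the readable protocol mostly gives no XmAb18087 resume dose, and following the day-based tables literally would skip a step-up level in Cohorts 2A, 3A, 2C and 3C

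*Protocol*

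**What the plan says.** **Hold and stop rules.** Under Protocol Section 10.3.1, a subject whose event meets AESC criteria "will have subsequent dosing held until recovery to baseline or ≤ Grade 2 following the AE". Permanent discontinuation follows when a drug-related toxicity above Grade 2 lasts more than 14 days, or when "2 consecutive doses are missed, the subject will be permanently discontinued from the study drug treatment". A subject who misses one dose and recovers may therefore resume. Rechallenge is barred after any Grade 4 toxicity.

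**Rules that name a dose.** There are two in the readable text. If the same AESC occurs on two infusions in a row, the subject "will be subsequently treated at one dose level lower than the dose at which the AE occurred" (10.3.1). After Grade 3 neurotoxicity the instruction is "Restart XmAb18087 at 75% of the previous dose" (11.3.3.4, repeated in Appendix C). For Grade 3 CRS or infusion reaction, 11.3.3.3 permits rechallenge after resolution but names no dose.

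**How doses are assigned.** Section 7.3 says "Part A dose levels are defined in Table 2", and refers to Table 4 for Part C. Both tables list one dose per numbered day. The Synopsis does the same: for Cohort 3A it places 4.0 µg/kg "on Days 22, 29, and 36 of the first cycle". Section 7.7 describes the intent: "Subsequent doses will then be escalated in steps", "in an effort to reduce the incidence and severity of CRS".

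**The concern.** Section 10.3.1 provides for a subject who misses exactly one dose and then resumes, but outside the two specific rules it does not say at what dose. The nearest written instruction is the day-based table. A site that follows it gives the dose listed for the day on which the subject returns, and in some cohorts that dose is two levels above the last one received.

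The step-up exists to limit CRS, and Section 11.3.2 says CRS is more likely after the first dose or a first escalated dose. The literal reading would give a step larger than any the tables plan to a subject who has just recovered from an AESC. Up to 25 sites could also resolve the ambiguity differently, which would blur the Safety Review Committee's judgement of whether a step-up regimen is tolerable.

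**Working it through.** The plan states no fold-change, so there is no figure of its own to reproduce. The check uses the doses in Tables 2, 3 and 4.

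**Inputs, Cycle 1, µg/kg on Days 1 / 8 / 15 / 22 / 29 / 36**
- 1A, 1C: 0.3 / 1.0 / 1.0 / 1.0 / 1.0 / 1.0
- 2A, 2C: 0.3 / 1.0 / 2.0 / 2.0 / 2.0 / 2.0
- 3A, 3C: 0.3 / 1.0 / 2.0 / 4.0 / 4.0 / 4.0
- 1B to 4B: Table 3

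**Formulas**
- Planned step = next scheduled dose ÷ current dose.
- Step after one held dose, calendar reading = dose listed for the next dosing day ÷ last dose received.
- Step after one held dose, sequence reading = the held dose ÷ last dose received.

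The largest planned step in any table is 1.0/0.3 = 3.33-fold.

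**One post-Day 1 dose held at a time**

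| Cohorts | Held | Calendar reading | Dose number | Level skipped | Sequence reading |
|---|---|---|---|---|---|
| 2A, 3A, 2C, 3C | Day 8 | 2.0/0.3 = 6.67 | 2nd | yes | 1.0/0.3 = 3.33 |
| 3A, 3C | Day 15 | 4.0/1.0 = 4.0 | 3rd | yes | 2.0/1.0 = 2.0 |
| 1A, 1C | Day 8 | 1.0/0.3 = 3.33 | 2nd | no | 3.33 |
| 2A, 2C | Day 15 | 2.0/1.0 = 2.0 | 3rd | no | 2.0 |
| 3A, 3C | Day 22 | 4.0/2.0 = 2.0 | 4th | no | 2.0 |

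In Part B no single held dose skips a level, and the largest step stays at 3.33-fold. Across the 10 run-in regimens, the calendar reading exceeds 3.33-fold in 4 + 2 = 6 cohort-by-day cases, all in four cohorts.

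**Protections in the six cases**
- The 6.7-fold step is the subject's second dose: premedicated (10.1.3) and followed by an inpatient stay of at least 48 hours (7.1).
- The 4-fold step is the third dose: premedicated, with at least 4 hours of observation (Table 7, footnote e). The cut to 2 hours needs four infusions at the subject's highest dose, so it cannot apply here. Four hours is also the minimum for planned escalations at dose 3 or 4.
- In every case, infusions should start before 2 PM if possible and a physician must be available for at least 24 hours (10.1.3). A crash cart and tocilizumab must be at hand, with continuous oximetry during observation (10.1.4).

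**Reach.** Section 7.7 enrols three subjects per cohort before the committee meets on advancing. SAP Section 5.1 reports two subjects in Part A and two in Part C, so Cohorts 2A and 2C could not have opened under that rule.

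**The case against.** The strongest reply is that the skip depends on the less protective reading. *Held* can mean deferred, Section 7.7 speaks of escalation in steps, and several protections are tied to dose order (the first two doses inpatient, the first four premedicated). That reading is reasonable, and a careful investigator would probably adopt it. It does not close the gap. Section 10.3.1 itself counts undelivered doses as missed, the cycle is fixed at 42 days with a Day 40 assessment, and no readable text says that a missed step is given later.

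A second reply is that the rule may sit in text that cannot be seen. Section 5.3 is blank, Sections 7.3, 10.1.1 and 10.1.4 have gaps, and the Pharmacy Manual is not provided. This stands as a limit. The gaps in 7.3 and 10.1.4 look like infusion duration and solution handling, but Section 5.3 cannot be judged. The readable part of 10.3.1 is where such a rule belongs.

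A third reply is that the trigger is narrow: a non-neurologic Grade 3 AESC, still above Grade 2 at the next weekly dose, recovered before a second miss, with the hold falling on one of two days. This also stands. Grade 3 CRS that resolves before the next dose misses nothing and is outside the point. The trigger is not empty, though. Section 7.8 defines some AESCs by persistence, such as Grade 3 or higher thrombocytopenia lasting at least 7 days, and dosing is weekly.

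A reader might infer that the protocol tells sites to skip a step, that a 3.3-fold safety limit is breached, or that the third-dose case is observed less closely than routine escalations. The documents support none of these. No text orders the skip, 3.3-fold is simply 1.0/0.3, and the 4-hour minimum is the ordinary one.

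**Conclusion.** The gap holds on the readable text and should be closed, with medium confidence. Under the calendar reading, six cohort-by-day cases give a larger step than any planned: 6.7-fold in four and 4-fold in two. Under the sequence reading the same cases give 3.3-fold and 2-fold.

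This rests on a single held dose, on neither specific dose-reduction rule applying, and on no rule existing in unseen text. The resumed doses of 2.0 and 4.0 µg/kg are themselves planned for these cohorts, so only the step is larger. A fold ratio is not a risk estimate, and the documents give no frequency for the trigger.

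It should not be read as a finding that any enrolled subject was exposed to a skipped step, because the affected cohorts could not have opened. The point concerns the plan as written, including any expansion (up to 22 subjects in Part A, up to 30 in Part C) had the recommended dose been a Cohort 2 or Cohort 3 regimen.

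**What to change.** Add one sentence to Section 10.3.1 and a footnote to Tables 2 and 4: step-up doses follow sequence and not calendar day; after a held or missed step the subject resumes no higher than that step; no step is skipped. State that the 75% rule after Grade 3 neurotoxicity and the one-level-lower rule after a repeated AESC keep precedence. If the rule already exists in text not available here, a cross-reference in 10.3.1 is enough.

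No extra subjects or procedures are needed. The cost is that an affected subject reaches target dose about one week later in Cycle 1: Day 22 instead of Day 15 in 2A and 2C, and Day 29 instead of Day 22 in 3A and 3C.
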